3.3. Protocol-Specific Discontinuation Criteria

GS-2829 and GS-6779 have been evaluated in nonclinical studies without any identified dose-limiting toxicity up to the highest proposed dose. In this first in human protocol, the following rules will guide early discontinuations from the study.

3.3.1. Criteria for Early Discontinuation for the Individual Participant From the Investigational Product

Administration of the investigational product should be discontinued in the following instances:

- If a participant experiences a Grade 3 or higher treatment-emergent AE (TEAE; excluding nausea, headache, measured grades of erythema and edema/induration alone) or confirmed Grade 3 or higher laboratory abnormality (except for those with a physiologic explanation for the events [eg, blood in urine occurring in a menstruating female, creatine phosphokinase elevation after strenuous exercise, triglyceride elevation that is nonfasting, etc]) considered clinically significant by the investigator and judged as related to the investigational product
- Any AE, laboratory abnormality or intercurrent illness which, in the opinion of the investigator, indicates that continued participation in the study is not in the best interest of the participant
- Participant request to discontinue for any reason
- Participant noncompliance
- Pregnancy during the study (refer to Appendix [11.4](#))
- Loss to follow-up
- Investigator discretion
- Discontinuation of the study by the sponsor

If a participant refuses to receive the remaining doses of investigational product as the result of an AE that is judged by the investigator as related to investigational product, an early termination (ET) visit should be completed, and every attempt should be made to retain the participant in the study to continue study evaluations. Following the receipt of any abnormal results believed to be related to investigational product at the ET visit, further testing should be repeated weekly or as often as deemed clinically appropriate by the investigator until the abnormality resolves, returns to baseline visit levels, or is otherwise explained.

If the participant withdraws consent from the study, the ET evaluations and/or procedures should be performed within 7 days of the decision to discontinue from the study.

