4.3. Phase 1b Virally Suppressed CHB Participant Inclusion/Exclusion Criteria

4.3.1. Inclusion Criteria

Phase 1b participants must meet all of the following inclusion criteria at screening (or as stated otherwise) to be eligible for participation in this study:

- 1) Have the ability to understand and sign a written ICF, which must be obtained prior to initiation of study procedures.
- 2) Assigned male sex at birth or female sex at birth (and be nonpregnant and nonlactating).
- 3) Participants assigned male at birth and participants assigned female at birth and of childbearing potential who engage in heterosexual intercourse must agree to use protocol-specified methods of contraception as described in Appendix 11.4
- 4) Be aged 18 through 65 years, inclusive, at enrollment.
- 5) Have a calculated BMI of ≤ 32.0 kg/m².
- 6) Documented evidence of CHB based on one of the following:
 - a) Positive HBsAg or HBV DNA at least 6 months prior to the screening visit; OR
 - b) Historical liver biopsy consistent with CHB infection available.

- 7) Quantitative HBsAg greater than the LLOQ and ≤ 5000 IU/mL at screening.
- 8) Have no evidence of advanced fibrosis by FibroScan (defined as FibroScan < 9 kPa within 6 months of screening). If a historical FibroScan is not available, this can be done at screening.
- 9) 12-lead ECG evaluations must be without clinically significant abnormalities as assessed by the investigator.
- 10) Nondiabetic with a hemoglobin A1c $< 6.5\%$.
- 11) Must be willing and able to comply with all study requirements.
- 12) Have a calculated CL_{cr} of at least 60 mL/min (using the Cockcroft-Gault method {[Cockcroft 1976](#)}) based on serum creatinine and actual body weight as measured for:
 - Participant assigned **male** at birth:
$$\frac{(140 - \text{Age [years]}) \times (\text{Weight [kg]})}{72 \times (\text{Serum Creatinine [mg/dL]})} = CL_{cr} \text{ (mL/min)}$$
 - Participant assigned **female** at birth:
$$\frac{(140 - \text{Age [years]}) \times (\text{Weight [kg]}) \times 0.85}{72 \times (\text{Serum Creatinine [mg/dL]})} = CL_{cr} \text{ (mL/min)}$$
- 13) Alanine aminotransferase $< 3 \times$ ULN; international normalized ratio (INR) \leq ULN; albumin ≥ 3.5 g/dL; direct bilirubin $\leq 1.5 \times$ ULN; platelets within the normal limit.

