- If the ALT elevation is confirmed, the central clinical laboratory will conduct reflex testing for HIV, HBV DNA, qualitative HBV serology (HBeAg and HBeAb; HBsAg and HBsAb), HAV IgM, HCV RNA, anti-HDV IgM, HDV RNA, HEV IgM, antinuclear antibody, antimitochondrial antibody, smooth muscle antibody, and liver/kidney microsome

Based on the results of the confirmatory tests, the following study treatment modifications are recommended.

Table 11. ALT Elevation Monitoring and Toxicity Management

Liver Toxicity Criteria	Action
Confirmed, ALT and or AST $\geq 10 \times$ ULN without evidence of hepatic toxicity as defined below	Cohort 5 to 7: Stop investigational product. Evaluate adherence to NA therapy and review recent HBV DNA results. Evaluate for other causes of hepatotoxicity. Participant must be monitored weekly or more frequently if clinically indicated until ALT returns to nadir. Investigative product may be restarted when ALT $< 5 \times$ ULN upon discussion with medical monitor. Dosing may also be reinitiated upon the recommendations of the SRT.
Persistent ALT and or AST $> 2 \times$ baseline and $\geq 5 \times$ ULN without evidence of hepatic toxicity, as defined below	Cohorts 5 to 7: Continue investigative product. ALT should be evaluated every 2 weeks or more frequently as clinically needed, until values return to nadir.
Confirmed ALT and or AST $> 2 \times$ nadir, with evidence of hepatic toxicity, defined as any one of the following confirmed laboratory abnormalities: Total bilirubin $> 2 \times$ baseline or nadir AND $> 2.5 \text{ mg/dL}$ in the absence of Gilbert's disease Elevated INR > 0.5 above baseline AND $>$ ULN Abnormal serum albumin $> 1 \text{ g/dL}$ decrease from baseline	Cohorts 5 to 7: Permanently discontinue investigational product. Evaluate adherence to NA therapy and review recent HBV DNA results. Evaluate for etiology of ALT elevation. Participant should be monitored weekly until ALT $< 5 \times$ ULN, and total bilirubin, INR, and albumin values return to normal or baseline levels. Liver biopsy may be performed based on investigator's clinical judgment to determine etiology.

ALT = alanine aminotransferase; AST = aspartate aminotransferase; DNA = deoxyribonucleic acid; HBV = hepatitis B virus; INR = international normalized ratio; NA = nucleos(t)ide analogue; SRT = Safety Review Team; TAF = tenofovir alafenamide; ULN = upper limit of normal

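### Phase 1b liver rules: Table 11's advice to continue dosing has no upper limit, so it overlaps the row that stops product and disagrees with Section 3.3.1

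*Protocol*

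**What the plan says.** Protocol Section 7.7.4 sets liver rules for Cohorts 5 to 7 in Table 11. Its lead-in says that "the following study treatment modifications are recommended". The three rows are:

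- **Row 1**, confirmed ALT and/or AST of at least 10 × ULN, no hepatic toxicity: "Stop investigational product. Evaluate adherence to NA therapy and review recent HBV DNA results". Restart is possible once ALT is below 5 × ULN, after talking to the medical monitor. In addition, "Dosing may also be reinitiated upon the recommendations of the SRT".
- **Row 2**, persistent ALT and/or AST above 2 × baseline and at least 5 × ULN, no hepatic toxicity: "Continue investigative product. ALT should be evaluated every 2 weeks or more frequently as clinically needed". No upper limit is printed.
- **Row 3**, a rise with hepatic toxicity (defined through bilirubin, INR or albumin): permanent discontinuation.

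Section 3.3.1 is the general rule for the individual participant: "Administration of the investigational product should be discontinued in the following instances". One instance is a "confirmed Grade 3 or higher laboratory abnormality" that is "considered clinically significant by the investigator and judged as related to the investigational product". The only exception is a physiologic explanation, and its examples concern menstruation, exercise and non-fasting triglycerides. ALT and AST are not mentioned, and there is no reference to 7.7.4.

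Neighbouring rules do make the link. Section 7.7.2 exempts ALT and AST from withholding at Grade 3. Section 3.3.3.2 leaves ALT rises without hepatic injury out of the cohort stopping rule and sends them to 7.7.4 and Table 11. Section 7.7.3 stops product permanently for confirmed, related Grade 4 abnormalities and points to 7.7.4.

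The Phase 1b entry limit (4.3.1, criterion 13) is "Alanine aminotransferase $< 3 \times$ ULN". There is no AST entry limit. Grading follows CTCAE Version 5.0 by reference (7.2.2, Appendix 11.6), without printed cut-offs.

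**The concern.** The same laboratory result can lead to opposite dosing decisions, depending on which row or section the site opens. These rules decide who is redosed after a liver enzyme rise in a first-in-human study, at about 15 Phase 1b sites. Such a rise is foreseeable, because the vaccines are meant to raise HBV-specific T cells and Section 1.1 describes those cells as acting against infected hepatocytes. The exemptions in 7.7.2 and 3.3.3.2 suggest that the authors expected some of these rises to reach Grade 3 and wanted the liver section to handle them. Section 3.3.1 was not brought into line.

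**Working it through.** The plan gives no figure to reproduce, so the check treats the rules as conditions on a value v, in multiples of ULN, with baseline b. The value is taken as confirmed and persistent, without hepatic toxicity. A result can be both confirmed and persistent, so those two words do not separate the rows.

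**Row 1 against row 2**

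- Row 1 applies when v ≥ 10. Row 2 applies when v ≥ 5 and v > 2b.
- Both apply when v ≥ 10 and v > 2b.
- The entry limit gives b < 3, so 2b < 6. The baseline condition is therefore always met at v ≥ 10, and the overlap starts at 10.
- Example: b = 1, v = 12. Since 12 ≥ 10, row 1 stops. Since 12 ≥ 5 and 12 > 2, row 2 continues.
- On a grid with b from 0.2 to below 3 and v up to just below 40, 100% of the cells meeting row 1 also meet row 2. With row 2 capped at v < 10, this falls to 0%.
- The baseline condition would separate the rows at v = 10 only if b ≥ 5.

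This holds for ALT while the Day 1 baseline is still inside the screening limit. It is not assured for AST, which has no entry limit.

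**Section 3.3.1 against row 2**

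This comparison also needs the rise to be judged related and clinically significant. Let g3 be the point at which Grade 3 starts. It is not printed, so it is assumed and varied. With row 2 capped at 10, the two rules disagree from max(g3, 5, 2b) up to just below 10.

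| Assumed g3 (× ULN) | Range of disagreement (× ULN) |
|---|---|
| 3 or 5 | 5 to <10 (from just under 6 if b is just under 3) |
| 8 | 8 to <10 |
| 10 or 12 | none |

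If Grade 3 were instead scaled to an abnormal baseline, starting above 5b (again an assumption), the range would need 5b < 10, so b < 2. On the grid, about 25% of the row 2-only cells with b above 1 and below 3 would then be affected. Grid shares are not patient probabilities.

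With row 2 uncapped, as printed, the range runs upward without end and is never empty.

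**What turns on it**

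- Phase 1b: 3 × 10 = 30 planned and 3 × 8 = 24 on active product.
- After dose k, discontinuing leaves 0 injections and continuing leaves the total minus k. That is 4 − k = 3 to 0 in Cohorts 5 and 6, and 6 − k = 5 to 0 in Cohort 7.
- These are ceilings that assume no missed dose.

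**The case against.** The best answer to the overlap is that row 1 must win. If row 2 applied at 10 × ULN and above, row 1 would have no effect on a persistent rise at any eligible baseline, so that reading is not sensible. This stands: what remains is a missing upper limit and an unstated precedence.

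On Section 3.3.1, the specific liver section plausibly governs over a general list, and 7.7.2 and 3.3.3.2 show that intent. The disagreement also needs relatedness, clinical significance and an unprinted cut-off. All this narrows the point. However, 3.3.1 still has neither an exception nor a pointer, and nothing ranks its *should* against Table 11's recommendation.

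A reader might infer that the protocol directs redosing at 10 × ULN or more. It does not. Table 11 only recommends, 3.3.1 also allows stopping in the participant's interest or at the investigator's discretion, and Section 7.7 brings in the medical monitor. A cautious outcome is likely.

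A reader might also infer that the restart routes in 7.7.4 contradict permanent discontinuation for Grade 4 in 7.7.3. Those routes say that dosing *may* resume. They are broad permissions, not an opposite order, and for Cohorts 1 to 4 and 8 they lie outside this point.

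Two limits remain. Appendix 11.5, to which Section 7.7 refers, has no visible content here and might settle the matter. Section 7.7.2 also withholds where 3.3.1 discontinues for other Grade 3 laboratory results, and an ALT/AST sentence would leave that untouched.

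**Conclusion.** In Phase 1b, for ALT/AST rises without hepatic toxicity, the printed dosing rules disagree in two places. The row 1 and row 2 overlap follows from the text and the ALT entry limit alone, and covers every persistent, confirmed ALT of at least 10 × ULN at an eligible baseline. The disagreement with 3.3.1 is conditional. It needs a related and clinically significant rise and, once row 2 is capped, a Grade 3 threshold below 10 × ULN. With hepatic toxicity, Table 11 discontinues and no conflict arises.

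The documents give no event rate, so the number of participants affected cannot be stated. Sample size and analysis are unaffected. This should be fixed because it is a safety rule in a first-in-human study, but it is a wording correction and not a demonstrated hazard.

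**What to change.** 1. In Table 11 row 2, change the criterion to *above 2 × baseline and at least 5 but below 10 × ULN*.
2. Add to Section 3.3.1: *In Cohorts 5 to 7, ALT/AST elevations below Grade 4 without hepatic toxicity as defined in Table 11 are managed per Section 7.7.4.* This brings 3.3.1 into line with 7.7.2 and 3.3.3.2. Confirmed, related, clinically significant Grade 4 rises stay under 7.7.3.

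Before adopting the second change, the sponsor should check it against Appendix 11.5 and against the individual discontinuation rules, which the history of Amendment 1 says were aligned to FDA requirements. If 3.3.1 has to stand without an exception, row 2 should be made to yield to it instead.

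The cost is a small protocol amendment with ethics committee approval (Section 9.2.1). It adds no visits, tests or data.

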7.7.5. Potential Immune-mediated Adverse Events on Study

Potential immune-mediated conditions (PIMMC) are AEs that include autoimmune diseases and other inflammatory and/or neurologic disorders of interest, which may or may not have an autoimmune etiology. PIMMCs have been reported in some vaccine studies and in the clinical use of some vaccines {[Tavares Da Silva 2013](#)}. For this study, any new onset or worsening of a preexisting PIMMC will need to be reported regardless of grade. A list of PIMMC is provided in Appendix [11.7](#).

8. STATISTICAL CONSIDERATIONS

Details of the statistical methods will be provided in the statistical analysis plan and the biomarker analysis plan, including any deviations from the original statistical analyses planned.

8.1. Analysis Objectives and Endpoints

Objectives and endpoints are listed in Section [2](#).

8.2. Planned Analyses

8.2.1. Interim Analysis

Prior to the final analysis, interim analyses may be conducted at the discretion of the sponsor and the results from these analyses may be submitted to regulatory agencies to facilitate the overall clinical program development or to scientific meetings or journals to disseminate the findings.

8.2.1.1. Dose-escalation Analysis

For the purpose of making the decision to escalate from the low- to high-dose level or to increase the number of doses (at the high dose) from 2 doses of each investigational product, to 3 doses of each investigational product (see Section [3.1](#)), interim analyses of relevant safety data will be conducted by Gilead. Safety assessments (eg, AEs, ECG, laboratory test results) will be displayed by cohort to facilitate these decisions while preserving the blind at the participant level.

Review of relevant safety data will be conducted by the SRT to facilitate the decision to escalate from the low to high dose; and to increase from 2 doses of each investigational product to 3 doses of each investigational product (high-dose level).

8.2.2. Final Analysis

The unblinded final analysis will be performed after all participants have completed the study, outstanding data queries have been resolved or adjudicated as unresolvable, and the data have been cleaned and finalized. The analysis of the primary endpoints will be conducted at the time of the final analysis.

8.3. Analysis Conventions

8.3.1. Analysis Sets

8.3.1.1. All Randomized Analysis Set

The All Randomized Analysis Set will include all participants randomized into the study after screening. This is the primary analysis set for safety listings.

8.3.1.2. Safety

The Safety Analysis Set will include all randomized participants who received at least 1 dose of investigational product. Participants who received treatment other than that to which they were assigned will be analyzed according to the treatment received.

The Safety Analysis Set is the primary analysis set for safety analyses. All data collected during the study will be included in the safety summaries.

8.3.1.3. Pharmacodynamics (Immunogenicity)

The Immunogenicity Analysis Set will include all randomized participants who received at least 1 dose of investigational product and have at least 1 nonmissing value for immunogenicity evaluation after administration of the investigational product.

8.3.2. Data Handling Conventions

Laboratory data that are continuous in nature but are less than the LLOQ or above the upper limit of quantification will be imputed to the value of the lower or upper limit minus or plus 1 significant digit, respectively (eg, if the result of a continuous laboratory test is less than 20, a value of 19 will be assigned; if the result of a continuous laboratory test is less than 20.0, a value of 19.9 will be assigned).

Missing data can have an impact upon the interpretation of the study data. In general, values for missing data will not be imputed. However, a missing pretreatment laboratory result would be treated as normal (ie, no toxicity grade) for the laboratory abnormality summary.

8.4. Demographic Data and Baseline Characteristics Analysis

Demographic and baseline measurements will be summarized, and descriptive statistics will be provided. Demographic summaries will include sex, race, ethnicity, and age at baseline. Baseline data will include a summary of body weight, height, BMI, and HBV genotype (for Phase 1b participants only). Additional baseline characteristics may be added, as applicable.

8.5. Safety Analysis

All safety data collected on or after the date that investigational product was first administered up to study completion will be summarized by population and treatment group according to the investigational product received. Data for the pretreatment period and up to study completion will be included in data listings.

8.5.1. Extent of Exposure

A participant's extent of exposure to investigational product data will be generated from the investigational product administration data. Exposure data will be listed.

8.5.2. Adverse Events

The analysis of data on safety and reactogenicity events will be based on the Safety Analysis Set. Data from participants receiving PBO in different cohorts may be combined within the same population for the final analysis.

Clinical and laboratory AEs will be coded using the current version of the MedDRA. System organ class, high-level group term, high-level term, preferred term (PT), and lower-level term will be attached to the clinical database.

Events will be summarized on the basis of the date of onset for the event. A treatment-emergent AE will be defined as:

- Any AE that begins on or after the date of first dose of investigational product and through the duration of the study; or any AE leading to investigational product discontinuation.

Summaries (number and percentage of participants) of treatment-emergent AEs (by system organ class, high-level term, if applicable, and PT) will be provided by population and treatment group using the current version of MedDRA.

- All TEAEs
- TEAEs of Grade 3 or higher
- TEAEs of Grade 2 or higher
- All treatment-related TEAEs
- Treatment-related TEAEs of Grade 3 or higher
- Treatment-related TEAEs of Grade 2 or higher
- All treatment-emergent SAEs
- All treatment-related treatment-emergent SAEs
- All TEAEs leading to premature discontinuation of any investigational product
- All TEAEs leading to temporary interruption of any investigational product

All AEs collected during the study will be presented in the data listings.

8.5.3. Laboratory Evaluations

Selected laboratory test data will be summarized using only observed data. Change from baseline at all scheduled time points will be summarized. Graded laboratory abnormalities will be defined using the grading scheme in Section 11.6.

The incidence of treatment-emergent laboratory abnormalities, defined as values that increase by at least 1 toxicity grade from baseline levels at any time after baseline evaluation through the duration of the study, will be summarized by population and treatment group.

Laboratory abnormalities that occur before the first dose of investigational product will be included in a data listing.

8.5.4. Other Safety Evaluations

Vital signs and ECG data will be summarized by population, treatment group, and visit.

8.6. Pharmacodynamic Biomarker Analysis (Immunogenicity)

The pharmacodynamic biomarker (immunogenicity) analysis will be based on the proportion of participants with investigational product-induced HBV-specific T-cell response, as determined by the IFN- γ ELISpot assay, and will be summarized by population and treatment group.

The magnitude of the total investigational product-induced HBV-specific T-cell response, as determined by the IFN- γ ELISpot assay, will be summarized by population and treatment group.

The immunoassay result listing will also be included.

8.7. Other Exploratory Biomarker Analyses

Biomarker analyses may include additional measurements of HBV-specific immune response including intracellular cytokine staining, anti-HBsAg antibodies, anti-HBsAg immune complexes, HBV-specific B-cells, and antivector neutralizing antibodies. Further analyses may include gene expression profiling, serum cytokine analysis, T-cell receptor repertoire sequencing, peripheral blood mononuclear cell (PBMC) single cell RNA sequencing, and PBMC cytometry by time of flight immune phenotyping. Data for each assay performed will be summarized by population and/or treatment group and postvaccination changes at defined time points calculated against the baseline. The details for the exploratory biomarker analyses will be described in a separate biomarker analysis plan.

8.8. Sample Size

The sample size in this study is determined based on practical considerations and empirical experience with similar types of studies. No formal power and sample size calculation was performed. Overall, a total sample size of approximately 80 participants (10 participants per cohort, (including 8 active and 2 PBO) is expected to provide a suitable assessment of the safety, tolerability, and immunogenicity of treatment with the investigational product.

